3.1 Objectives

3.1.1 Main objective:

- To evaluate the safety and tolerability of PRO-185 ophthalmic solution in ophthalmologically healthy subjects.

3.1.2 Specific objectives:

- To evaluate the safety of PRO-185 ophthalmic solution by measuring the incidence of subjects who present an increase of > 5 mmHg in intraocular pressure after 20 minutes of application compared to the initial value.
- To evaluate the safety of PRO-185 ophthalmic solution by measuring the incidence of subjects experiencing a heart rate variation of >15 beats per minute 20 minutes after application.
- To evaluate the safety of PRO-185 ophthalmic solution by measuring the incidence of subjects with an increase in systolic blood pressure of >15 mmHg or >10 mmHg in diastolic blood pressure 20 minutes after application.
- To assess tolerability by the incidence of grade 3 and 4 conjunctival hyperemia.
- To assess tolerability by the incidence of pharmacological mydriasis.
- Evaluate tolerability by the incidence of expected and unexpected adverse events.

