3.2 Hypothesis

H_0 = PRO-185 ophthalmic solution is safe and tolerable for ophthalmic use, as it occurred in 20% or less of subjects with any of the following adverse events: increased intraocular pressure (IOP >5 mmHg), heart rate variation (>15 bpm), increased systemic blood pressure [>15 mmHg systolic (SBP) or >10 mmHg diastolic (DBP)], pharmacological mydriasis, or grade 3 and 4 conjunctival hyperemia.

$$H_0: p - p_0 \leq \delta$$

H_1 = PRO-185 ophthalmic solution is not safe or tolerable for ophthalmic application because more than 20% of subjects experienced any of the following adverse events: increased IOP (>5 mmHg), heart rate variation (>15 bpm), increased systemic blood pressure [>15 mmHg systolic (SBP) or >10 mmHg diastolic (DBP)], pharmacological mydriasis, or grade 3 and 4 conjunctival hyperemia.

$$H_1: p - p_0 > \delta$$

Comparisons will be made between pre- and post-treatment measurements from visits 1 and 2, and between measurements from the baseline visit (before PT application) and measurements from the

final visit. Only one of the adverse event values described in the hypothesis need be abnormal with a frequency >20% between the comparisons (pre-treatment with post-treatment; or pre-PT baseline with values from the final visit) for the null hypothesis to be rejected.

4. Study design

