5.2 Criteria for elimination and/or substitution of subjects

5.2.1 Elimination criteria

- Withdrawal of informed consent.
- Major deviation from the protocol that could impact the integrity of the results.
- Presentation of an adverse event, whether or not related to the investigational product, which, in the opinion of the PI and/or the sponsor, could affect the subject's ability to safely continue the study procedures.
- Non-tolerability or hypersensitivity to any of the compounds used during the tests.
- Non-tolerability or hypersensitivity to the investigational product.

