7.4.5 Description of the variables, methods and scales for their measurement

7.4.5.1 Intraocular pressure

Tonometry is the objective measure of IOP, based primarily on the force required to flatten the cornea, or the degree of corneal depression produced by a fixed force. Goldman tonometry is based on the Imbert-Fick principle. [34]

Tonometry will be performed after instillation of topical anesthetic with fluorescein and the use of a cobalt blue filter (after assessing surface staining). Two readings will be taken, and the average will be recorded in the clinical record. The average will be recorded in the eCRF .

Management as AEs: IOP peaks ≥ 24 mmHg should be reported as AEs, as well as increases in intraocular pressure greater than 5 mmHg between evaluations before and after application of the investigational product (visits 1 and 2).

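### Protocol 3.2 states its hypotheses per subject but rejects per comparison, so no comparison need exceed 20% even when more than 20% of subjects had the event

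*Protocol*

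**What the plan says.** Protocol 3.1.2 sets the objectives as incidences of subjects, for example "measuring the incidence of subjects who present an increase of > 5 mmHg in intraocular pressure" 20 minutes after application. Section 3.2 follows this in H1, which calls the product not safe "because more than 20% of subjects experienced any of the following adverse events".

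The same section then says how the data are to be read. "Comparisons will be made between pre- and post-treatment measurements from visits 1 and 2", and the pre-dilation baseline is compared with the final visit. H0 is rejected on this condition: "Only one of the adverse event values described in the hypothesis need be abnormal with a frequency >20% between the comparisons". The synopsis repeats the rule.

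Some primary events are also adverse events. Section 7.4.5.1 has the investigator report "increases in intraocular pressure greater than 5 mmHg between evaluations before and after application of the investigational product (visits 1 and 2"). Sections 7.4.5.4 and 7.4.5.5 do the same for a pupil change above 2 mm and for grade 3 or 4 hyperemia. Section 5.2.1 lists two relevant grounds for elimination. One is an adverse event of any cause that the investigator or sponsor thinks "could affect the subject's ability to safely continue the study procedures". The other is "Non-tolerability or hypersensitivity to the investigational product".

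Protocol 10.3.2.1 analyses everyone who received a dose, and 10.4 provides for no imputation. Neither these sections nor SAP 6.2 says how a subject is counted across visits, or what the denominator of each comparison is.

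**The concern.** The hypothesis and its rejection rule measure different things. The hypothesis concerns the share of subjects who had the event. The rule concerns the share within a comparison. When different subjects react on different occasions, the second can stay at or below 20% on every occasion while the first is well above it.

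Producing a safety verdict is the purpose of this trial. One dataset could support two opposite verdicts, both traceable to 3.2. The choice between them would be made by sponsor staff after open-label data have been seen.

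Elimination after an adverse event adds a second, smaller issue. A visit 1 case who leaves has no visit 2 pre/post reading, so later comparisons are made among the subjects who did not react at visit 1.

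**Working it through.** **Inputs from the documents.** 22 planned subjects (synopsis; 10.1.2), a 20% limit (3.2), and three comparisons: visit 1 pre/post, visit 2 pre/post, baseline against final.

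**The plan's own figure.** Protocol 10.1.2 gives 18 subjects, and 18 × 1.2 = 21.6, so 22. The expected proportion p is not stated as a number. With an assumed p = 0.10, p₀ = 0.20, δ = 0.10 and 80% power, n = 0.10 × 0.90 × [(1.96 + 0.84)/(0.10 − 0.30)]² = 17.7, so 18. The variance printed in the protocol, p(1 − 0.2), gives 15.7 at p = 0.10 and returns 18 at p = 0.107.

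**Most subjects affected with no comparison above 20%** (one event type):

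- With 22 at risk the largest allowed count is 4 (4/22 = 18.2%; 5/22 = 22.7% exceeds 20%).
- Nobody withdrawn, different subjects each time: 4 + 4 = 8/22 = 36.4% over visits 1 and 2. Adding 4 others at the final comparison gives 12/22 = 54.5%.
- Visit 1 cases withdrawn: 18 remain and 3/18 = 16.7% is allowed, so 4 + 3 = 7/22 = 31.8%. Adding 3 at the final comparison (3/18, or 3/15 = 20.0%) gives 10/22 = 45.5%.
- Visits 1 and 2 pooled per subject, with only the final comparison separate: 8/22 without withdrawal, 7/22 with it.

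**How often the readings disagree.** Assumptions: 22 subjects, visits 1 and 2 only, the same risk q at each visit, independent within subject. Withdrawal means that every visit 1 case leaves. Under independence the number with at least one event is binomial with probability 1 − (1 − q)². The table comes from exact enumeration. The two middle columns give the chance that both visits are at or below 20% while more than 20% of the 22 had the event.

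| q per visit | 1 − (1 − q)² | No withdrawal | Withdrawal | Chance of at most 4/22 with any event |
|---|---|---|---|---|
| 5% | 9.8% | 4.9% | 4.9% | 94.3% |
| 10% | 19.0% | 28.9% | 28.2% | 59.1% |
| 15% | 27.8% | 37.1% | 35.4% | 22.7% |
| 20% | 36.0% | 23.5% | 22.2% | 5.9% |

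At 5% and 10% the underlying two-visit incidence is itself below 20%. There the figures show how often the two readings of one sample disagree, not how often an unsafe product passes.

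**Where withdrawal matters.** Suppose the 4 visit 1 cases would react again and 3 new cases appear. If all stay, visit 2 is 7/22 = 31.8% and H0 is rejected. If the 4 leave, visit 2 is 3/18 = 16.7% and it is not. In a simulation with 15% risk per visit (200,000 trials), disagreement rises with withdrawal from 26.5% to 33.5% at a within-subject correlation of 0.3, and from 13.3% to 22.3% at 0.6.

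**The case against.** The best defence is that the conflict is only one of reading. H1 taken literally already calls 7/22 or 8/22 not safe. The parenthesis after the rejection sentence names two types of comparison, so visits 1 and 2 may be meant to be pooled. The IOP, heart rate and blood pressure objectives are tied to 20 minutes after application, which fits an incidence per application. The safety population is everyone dosed, so the denominator may stay at 22. Mydriasis is already defined against any later measurement. IOP rises, mydriasis and hyperemia would in any case appear in the adverse event tables.

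Much of this is fair. It shows that 3.2 does not force a wrong verdict. It does not close the gap. Pooling visits 1 and 2 still leaves the final comparison separate, and a fixed denominator of 22 still allows 8/22. A definition of mydriasis does not say how the 20% is counted. Adverse event tables report events but do not apply the rule.

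A reader might infer that withdrawal of visit 1 cases is what hides the events. The documents do not support that. With independent visits, withdrawal slightly lowers the chance of disagreement (35.4% against 37.1% at 15% risk) and lowers the two-visit ceiling from 8 to 7 subjects. Elimination is also discretionary. Heart rate and blood pressure changes become adverse events only at absolute limits (7.4.5.2, 7.4.5.3), so the chain from event to elimination is direct only for IOP, mydriasis and hyperemia.

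**Conclusion.** The point holds as a conflict inside Protocol 3.2 between hypotheses worded per subject and a rejection sentence worded per comparison. Followed as written, the rejection sentence can leave H0 standing with 8/22 (36.4%) of subjects affected over the two dosing visits, or 7/22 (31.8%) if visit 1 cases leave. The SAP does not resolve it: it gives no comparison rule, and its use of 10% in place of 20% is a separate discrepancy.

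The ceilings are plain arithmetic. The probabilities depend on an assumed per-visit risk that the documents do not give, and they range from about 5% to 37% over risks of 5% to 20%. Withdrawal is a secondary contributor that matters when the same subjects tend to react again. It would go too far to say that the trial will declare an unsafe product safe, because H1 read literally gives the opposite verdict on the same data. The change should be made before the data are analysed.

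**What to change.** In Protocol 3.2 and 10.3.2.1 and in SAP 6.2, define for each of the five primary events the number of subjects with that event in at least one planned comparison, divided by all dosed subjects. Base the 20% verdict on that proportion. A subject who has had the event stays counted after leaving the study. Show the frequency in each comparison, with the number at risk, as supportive tables. The clinical withdrawal rule is unchanged.

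This needs wording only and no new data, but it does change what the limit demands. At an assumed independent 10% risk per comparison, the chance of at most 4/22 subjects with the event is about 59% over the two dosing visits (incidence 19.0%). Over all three comparisons it is about 25% (1 − 0.9³ = 27.1%). The sponsor should therefore confirm that 20% is meant for this subject-level incidence, and check that the limit and the 22 subjects still suit it. If an incidence per application is what is wanted, H0, H1 and the objectives should say so.

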10.1.2 Size calculation

PRO-185 ophthalmic solution is expected to present in less than 20% of subjects any of the following AEs: increased IOP (>5 mmHg), heart rate changes (>15 bpm), increased systemic blood pressure (>15 mmHg in SBP or >10 mmHg in DBP), pharmacological mydriasis or grade 3 and 4 conjunctival hyperemia, 20 minutes after its application with respect to its initial value.

The sample size was calculated using the equation for a non-superiority proportion [53]. This equation is useful for non-inferiority/superiority tests, if we want to test whether a proportion (p) is not superior to a reference value, p_0 (20% in this case). The idea is that statistically significant differences between the proportion and the reference value cannot be of interest unless the difference is greater than a threshold δ (10% in this case). This type of calculation is useful in clinical studies where the value of δ is chosen based on clinical judgment and knowledge of the subject.

The hypothesis test is:

$$H_0: p - p_0 \leq \delta$$

$$H_1: p - p_0 > \delta$$

Equations

The calculation to estimate the sample size and power was performed using an online tool and following the equations [53]:

$$18 = p(1 - 0.2) \left(\frac{1.96 + z_{1-\beta}}{p - 0.2 - 0.1} \right)^2$$

$$1 - \beta = \Phi(z - 1.96) + \Phi(-z - 1.96), z = \frac{p - 0.2 - 0.1}{\sqrt{\frac{p(1 - 0.2)}{18}}}$$

Where:

n is the sample size (18)

p₀ is the reference value (0.20)

Φ is the function of the standard normal distribution

Φ⁻¹ is the function of the standard normal distribution

α is the Type I error (1.96)

β is the Type II error, which means that, 1-β (1-0.8) is the power

δ is the test margin (0.10)

According to the previous calculation, 18 subjects are estimated, increasing the calculation by 20% considering possible losses, 22 subjects are estimated to contribute OA to the study. This calculation is in accordance with the average number of subjects used in the clinical studies reviewed in the search performed in PubMed and Web of Science (24 subjects), where the incidence of adverse events was similar to that expected in this study.

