### 3.2 Study Hypothesis

#### 3.2.1 Null hypothesis (H0)

PRO-185 ophthalmic solution is not safe and tolerable for ophthalmic use because more than 10% of subjects experienced any of the following AEs: increased IOP (>5 mmHg), changes in HR (>15 bpm), increased systemic blood pressure (>15 mmHg SBP or >10 mmHg DBP), pharmacological mydriasis, or grade 3 and 4 conjunctival hyperemia.

$$H_0 = p - p_0 \leq \delta$$

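### The plan does not settle whether the 20% limit applies to subjects with any of the five events or to each event type alone, so a safe verdict need not mean that 20% or fewer of subjects had an event

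*Protocol*

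**What the plan says.** Protocol 3.2 (repeated in synopsis 1.1) describes the safe state, H0, as "20% or less of subjects with any of the following adverse events", and the unsafe state, H1, as "more than 20% of subjects experienced any of the following adverse events". Both are written with one symbol p. The five events are a rise in intraocular pressure, a change in heart rate, a rise in blood pressure, pharmacological mydriasis, and grade 3 or 4 hyperemia. Protocol 10.1.2 uses the same form for the planning assumption: "less than 20% of subjects any of the following AEs". It computes n = 18 for one proportion and adds 20% for losses, giving 22.

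The decision sentence that follows H0 and H1 in 3.2 reads "Only one of the adverse event values described in the hypothesis need be abnormal with a frequency >20" (per cent), judged across the comparisons "pre-treatment with post-treatment; or pre-PT baseline with values from the final visit) for the null hypothesis to be rejected".

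The change history explains that the words *any of* were inserted to show that one of the listed events reaching the stated frequency is enough. Protocol 3.1.2 sets incidence objectives event by event, 7.4.1 lists five primary variables, and 10.3.2.1 analyses the variables one at a time.

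SAP 3.2.1 uses the *any of* form with a different figure, "more than 10% of subjects experienced any of the following AEs". SAP 3.2.2 reads more naturally as a limit on each event. The SAP has no counterpart to the protocol's decision sentence. Neither document defines or analyses a yes/no any-event outcome per subject.

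**The concern.** Taken literally, H0, H1 and the sample size concern the proportion of subjects with at least one of the five events. The decision sentence concerns five proportions, one per event type. Under the second, different subjects with different events are never added together, so the rule does not bound the first quantity.

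This matters because the decision sentence produces the trial's main conclusion. If the product passes on each event type, a report that then repeats the H0 wording would claim something the rule did not test. Two analysts, one following the literal H0 and the other the decision sentence, could reach opposite verdicts on the same data. If the choice were made after the results were seen, it could decide the outcome.

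**Working it through.** **Inputs.** Planned subjects 22 and evaluable subjects 18 (protocol 1.1 and 10.1.2); limit 20% (3.2); p0 = 0.20, margin 0.10, z = 1.96, power 0.80 (10.1.2); five event types (3.2). The protocol gives no number for the true p. I assume 0.10, the adverse event proportion in SAP 4.1.

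**1. The plan's own figure.** n = p(1 − p)[(z_α + z_β)/(p − p0 − δ)]² = 0.10 × 0.90 × [(1.96 + 0.84)/(0.10 − 0.20 − 0.10)]² = 0.09 × 14² = 17.6 (17.66 with unrounded z values), rounded up to 18. Then 18 × 1.2 = 21.6, rounded up to 22. The protocol prints the variance term as p(1 − 0.2), which gives 15.7, or 16. So 18 is reproduced with p(1 − p) and p = 0.10, and it is a calculation for one proportion.

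**2. What each rule allows.** 0.20 × 22 = 4.4, so 4 subjects (18.2%) pass and 5 (22.7%) do not.
- Any-event rule: at most 4 of 22 subjects may have an event.
- Per-event rule: 4 of 22 is allowed for each type. With no subject counted twice and one frequency per type, 5 × 4 = 20 of 22 (90.9%) may have an event.
- With 18 evaluable: 3 of 18 against 5 × 3 = 15 of 18 (83.3%).

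**3. How far the rules part in less extreme cases.** Assume five independent events, each with true rate q, n = 22, one comparison, and a verdict taken from observed counts:
- true any-event rate = 1 − (1 − q)⁵
- P(safe, per event) = [P(Bin(22, q) ≤ 4)]⁵
- P(safe, any event) = P(Bin(22, 1 − (1 − q)⁵) ≤ 4)

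| Assumed q per event | True any-event rate | P(safe), per event | P(safe), any event |
|---|---|---|---|
| about 2.1% | 10.0% | >0.999 | 0.94 |
| 5% | 22.6% | 0.98 | 0.42 |
| 8% | 34.1% | 0.87 | 0.08 |
| 10% | 41.0% | 0.73 | 0.02 |

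The documents give no rates for the individual events, so q is an assumption shown over a range. The first row makes the any-event rate equal to the 10% that reproduces n = 18. There the two rules nearly agree. In the other rows the true any-event rate is already above 20%, and the per-event rule still usually returns a safe verdict.

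**The case against.** The strongest reply is that there is one rule here and that the sponsor has explained it. The change history says what *any of* was meant to convey, and the decision sentence directly after H0 and H1 spells it out. The objectives, the list of primary variables and the planned tests all treat the events separately, and SAP 3.2.2 fits the same reading. Separate limits per event are a legitimate choice in Phase I. This stands: a reader might infer that the documents flatly contradict themselves, or that the trial was meant to be decided on a composite, and they support neither. No passage sets up a composite.

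A reader might also take 20 of 22 as a likely result. It is not: it needs exactly four subjects for every event type and no subject with two events. Nor is it a fixed ceiling, since if the limit is judged separately within each comparison, all 22 could have an event. Events that tend to occur together, such as changes in heart rate and blood pressure, would narrow the gap. At the 10% planning rate the choice hardly affects the verdict.

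Finally, a high overall burden need not stay hidden. Adverse event incidence is a secondary outcome, and several of the five findings must be recorded as adverse events (7.4.5). That helps visibility but does not enter the verdict.

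The reply does not remove the ambiguity in the current wording of H0 and H1, the single p behind n = 18, or the fact that per-event limits leave the overall share of subjects with an event unbounded.

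**Conclusion.** The concern holds as an unresolved ambiguity about which proportion decides. The per-event reading is the apparent intent, but H0, H1 and 10.1.2 can be read literally as the any-event share. A safe verdict under the decision sentence does not support the statement that 20% or fewer of subjects had any of the events.

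The size depends on rates the documents do not give. Under independence, one comparison and n = 22, the gap in the probability of a safe verdict is about 0.06 at 10% overall, 0.56 at 5% per event (0.98 − 0.42) and 0.79 at 8% per event (0.87 − 0.08).

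The point concerns only how event types are combined. How visits are combined, the boundary implied by p0 plus the margin, and the SAP's 10% figure are separate matters, and settling them would not settle this one.

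**What to change.** Before analysis, state in protocol 3.2, 10.1.2 and 10.3.2.1 and in SAP 3.2 which proportion decides the verdict.

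- **If per event (the apparent intent):** reword H0 and H1 so that safe means no single event type exceeds the limit. State that n = 18 was computed for one proportion, and that the verdict sets no limit on the overall share of subjects with an event. Report the per-subject any-event rate with an exact confidence interval beside the five event rates.
- **If composite:** define one yes/no outcome per subject, use it for the verdict, and report the five rates beneath it.

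Either route costs wording in both documents and one extra tabulation, with no new data. The any-event rate cannot be lower than the highest single event rate, so it will usually look less favourable. Under the composite route the verdict itself could change.

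### The stated power is for one proportion tested against 30%; it does not describe the rule that any one of 10 to 15 observed proportions above 20% ends the claim of safety

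*Protocol*

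**What the plan says.** Protocol 3.2 lists five events: a rise in intraocular pressure, a change in heart rate, a rise in blood pressure (systolic or diastolic), pharmacological mydriasis, and grade 3 or 4 conjunctival hyperemia. The null hypothesis is that the product is safe and tolerable. On the comparisons it says: "Comparisons will be made between pre- and post-treatment measurements from visits 1 and 2", and it adds baseline against the final visit. The rejection rule follows: "Only one of the adverse event values described in the hypothesis need be abnormal with a frequency >20% between the comparisons". The Change History shows that the per-event reading is deliberate, since version 2.0 inserted wording to make clear that one event suffices.

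Protocol 10.1.2 then sizes the trial: "The sample size was calculated using the equation for a non-superiority proportion". The stated purpose is to "test whether a proportion (p) is not superior to a reference value, p_0 (20% in this case"), with a margin of 0.10 and a critical value of 1.96. Power appears only in this line: "β is the Type II error, which means that, 1-β (1-0.8) is the power". The result is 18, raised by 20% to 22.

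Protocol 10.3.1 gives a significance level of 0.05. Neither document mentions several proportions, their correlation, a joint probability or a multiplicity adjustment.

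The SAP differs. Section 3.2 uses 10% rather than 20% and makes 'not safe' the null hypothesis. Section 4.1 bases the calculation on 10%. Section 4.2 expects each event in fewer than 10% of subjects and prints its formula in symbols, with no value for power.

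**The concern.** The calculation concerns one proportion, while the verdict depends on many. Each additional proportion is another chance for an acceptable product to cross 20% by luck in a sample of about 20. A reader of 10.1.2 would take the trial to have an 80% chance of reaching the right conclusion for a product that behaves as planned. No such figure has been worked out for the rule in 3.2.

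There is a second mismatch. The formula tests against the reference value plus the margin, 20% + 10% = 30%, whereas the verdict compares an observed proportion with 20% and uses no margin. At stake is the primary conclusion: the plan does not tell the sponsor or an ethics committee how often the trial would label an acceptable product unsafe.

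**Working it through.** **Inputs.** From Protocol 10.1.2: p0 = 0.20, δ = 0.10, z = 1.96, n = 18, then 22. From 3.2: five events; three comparisons (visit 1, visit 2, baseline to final) or two if visits 1 and 2 are pooled. Inferred: power 0.80, read from the line that prints 1-0.8, and true rate p = 0.10, which the protocol does not state.

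**Step 1: reproduce the 18.** n = p(1 − p) × [(z + z_power)/(p − p0 − δ)]² = 0.10 × 0.90 × [(1.96 + 0.842)/(0.10 − 0.30)]² = 17.66, rounded up to 18. Power at n = 18 is 0.807. Other readings miss: p = 0.20 gives 125.6, z = 1.645 gives 13.9, power 0.20 gives 2.8, and the variance as printed in the protocol, p(1 − 0.2), gives 15.7. So 18 is a one-proportion figure for a true 10% against 30%.

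**Step 2: one proportion under the actual cut.** With n = 22, at or below 20% means at most 4 events (4/22 = 18.2%; 5/22 = 22.7%). With n = 18 it means at most 3 (3/18 = 16.7%; 4/18 = 22.2%). At a true 10% the exact binomial probabilities are 0.938 and 0.902. Neither is 0.80, so the stated power does not fit the cut even before multiplicity.

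**Step 3: all proportions.** Assume that every event has the same true rate in every comparison and that the proportions are independent. Then P(safe verdict) = P(one passes)^k, with k = 10 or 15. For example, at 10% and n = 22, 0.9379^10 = 0.53 and 0.9379^15 = 0.38.

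| True rate | n | One proportion | 10 proportions | 15 proportions |
|---|---|---|---|---|
| 10% | 22 | 0.938 | 0.53 | 0.38 |
| 10% | 18 | 0.902 | 0.36 | 0.21 |
| 7% | 22 | 0.984 | 0.85 | 0.78 |
| 7% | 18 | 0.967 | 0.71 | 0.60 |
| 5% | 22 | 0.996 | 0.96 | 0.94 |
| 5% | 18 | 0.989 | 0.90 | 0.85 |

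**Step 4: correlation.** Measurements on the same subject will be positively correlated, which raises these figures. In simulations at a true 10% with a Gaussian latent variable, moderate correlation (a common value from 0.2 with 15 proportions to 0.6 with 10) gave about 0.44 to 0.66 at n = 22 and 0.30 to 0.55 at n = 18. For 15 proportions, a wider set (latent correlation 0.3 to 0.8, either within each event only or across all) gave 0.39 to 0.69 and 0.24 to 0.59. Complete dependence would return the one-proportion values of 0.94 and 0.90.

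**The case against.** The strongest reply is that the size of the problem rests on a rate the protocol never states. The 10% is solved back from 18, and SAP 4.2 expects less than 10%, so it is closer to a ceiling than a forecast. A uniform 10% across all five events is also doubtful on the background sections. Protocol 2.2.1 describes imidazole derivatives as less prone than phenylephrine to cause mydriasis, and Protocol 2.3.3 reports no change in graded hyperemia in 30 volunteers on a stronger solution, although 6.6% had mild red eyes. This stands: at 5% everywhere the chance of a safe verdict is at least 0.85 in every row above. It limits the size of the effect but not the mismatch. If only heart rate and blood pressure ran at 10% (six proportions) and the rest were near zero, the chance would still be 0.9379^6 = 0.68 at n = 22 and 0.9018^6 = 0.54 at n = 18.

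A second reply is that the rule is protective. Because the null hypothesis is 'safe', a false verdict of 'not safe' is a Type I error, and the same rule makes a real excess easier to detect. That is correct, and it is a good reason to keep the rule.

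Three stronger readings are tempting, and the documents do not support them:

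- A reader might take one figure from the 10% rows as the joint power of the trial. The rates, the correlations and the number of comparisons are all unstated, and the quantity is one minus a Type I error rather than power in the protocol's own terms.
- A reader might conclude that the trial is too small. The protocol's formula would need about 39 to 40 evaluable subjects for 80% joint power over 15 independent proportions at 10%, but neither document commits to 80% jointly.
- A reader might think that naming one decision variable would restore the 80%. It would not, because the formula tests against 30% and the verdict cuts at 20%. It would also weaken a safety rule that was strengthened on purpose.

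**Conclusion.** The concern holds in a limited form. The power in Protocol 10.1.2 belongs to one proportion tested against 30%. It describes neither the any-one rule in 3.2 nor the observed 20% cut, and neither document gives a figure that does. This conclusion needs no assumption about rates.

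The consequence does depend on assumptions. At the 10% that reproduces the sponsor's own sample size, a safe verdict is close to a coin toss or worse if the proportions are independent, and it stays below 0.70 in every correlated case reported above. At 5% it is likely. The count of 10 or 15 is itself open, because 3.2 does not say whether visits 1 and 2 are judged separately; nor do the documents say whether the two eyes are counted separately. The 80% is read from an unclear line, though it is the value that returns 18.

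**What to change.** 1. Reconcile the documents first. The protocol uses 20% with 'safe' as the null hypothesis; SAP 3.2 and 4 use 10% with 'not safe' as the null. No joint figure means anything until one threshold and one direction are fixed. State at the same time whether visits 1 and 2 are counted separately.
2. Keep the any-one rule. In Protocol 10.1.2, say that the 80% applies to one proportion with a true rate of 10% tested against 30%. Add the probability of a safe verdict under the actual rule, as a table over true rates of 5% to 10%, 10 to 15 proportions, n = 18 and 22, and stated correlations. Carry the agreed text into SAP 4.2.
3. Report each event-by-comparison proportion with an exact 95% confidence interval, so that a reader can tell a narrow crossing of 20% from a clear excess.

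The cost is protocol and SAP wording plus a short calculation. No subjects or visits are added. The stated figure becomes less favourable at rates near 10%.
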